- l. Mean Daily Glucose Profile: blood sample for plasma glucose level will be collected: 30 minutes before and immediately prior to AM meal, 30, 60, 90, 120 and 180 minutes after the start of the AM meal; immediately prior to the midday meal, 60, 120 and 180 minutes after the start of the midday meal; immediately prior to the evening meal, 60, 120 and 180 minutes after the start of the evening meal; approximately at 11:00 PM; 0300 AM and 0730 (immediately prior to the AM meal). On days when mean daily glucose profiles are being collected meals will be given at approximately 08:00 AM, 12:00 PM and 6:00 PM. Subjects will have 30 minutes to finish the meal and must consume the entire meal. Collection times are from the start of the meal.
- m. 24 hour ambulatory blood pressure monitoring: blood pressure assessments will be initiated in the AM on scheduled days and will be initiated at approximately the same time for a subject throughout the duration of the study.
- n. A peripheral IV or heplock may be placed upon admission to the CRU and will be maintained according to site standards. The PIV/heplock will be removed prior to discharge.
- o. Confirm subject is using appropriate contraception methods per [Sections 4.4.3.2](#) and [4.4.3.3](#) for methods and duration.
- p. On Day 36 and Day 64 only the following tests from the chemistry panel are to be performed: ALT, AST, GGT, LDH, alkaline phosphatase, total bilirubin, direct bilirubin, indirect bilirubin and CK.
- q. Dosing window: The dosing windows for Day 29 or Day 57 may be extended to ± 2 days to allow for evaluation of ALT/AST if subject experiences $\geq 3 \times$ ULN, ALT or AST following the Day 1 dose. See [Section 3.3](#).
- r. Screening ADA sample collected only from subjects who participated in the SAD cohort and want to participate in the MAD portion as well.

TABLE OF CONTENTS

LIST OF TABLES	24
1. INTRODUCTION	25
1.1. Indication.....	25
1.2. Background	25
1.2.1. Non-Clinical Toxicology	26
1.3. Rationale.....	27
1.3.1. Study Rationale.....	27
1.3.2. Preliminary Unpublished Data (blinded).....	28
1.3.3. Dose Rationale.....	32
2. STUDY OBJECTIVES AND ENDPOINTS	34
2.1. Objectives.....	34
2.1.1. Primary Objective.....	34
2.1.2. Secondary Objectives	34
2.1.3. Exploratory Objectives	34
2.2. Endpoints.....	34
2.2.1. Primary Endpoints	34
2.2.2. Secondary Endpoints	34
2.2.3. Exploratory Endpoints	34
3. STUDY DESIGN.....	35
3.1. Study Overview	35
3.2. Planned Number of Subjects	37

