For dose escalation, the decision to proceed to a higher dose will be made by the Pfizer study team and the Investigators after review of the available safety and tolerability data after 80% of the subjects in the previous cohort have received one dose and have been followed for 14 days post first dose. Enrollment in the previous cohort must be completed before initiating enrollment in a new cohort. If ≤ 2 subjects in a cohort discontinues the study prior to reaching Day 15, for reasons other than safety (eg, withdraw of consent), the subject(s) will be included in the dose escalation data review and do/does not need to be replaced for the purposes of determining dose escalation. The order of MAD regimen cohorts may change depending on the ongoing review of safety/PK data but at no time will doses be administered that exceed the PK exposure determined in the SAD portion. Dose escalation will be terminated based on the following criteria:

- Two (2) or more subjects receiving PF-06293620 drug (but not placebo subjects) develop similar clinically significant laboratory, ECG or vital signs abnormalities, or severe AEs in the same organ class, indicating dose-limiting toxicity as outlined in [Table 3](#) (Exception: dose escalation will be terminated if one (1) subject experiences ≥ 2 hypoglycemic events of CTCAE Grade ≥ 3 which do not meet SAE criteria; see [Table 7](#)).
- The limit of safety and/or tolerability has been reached.
- If dose escalation in the single ascending dose is terminated AND the exposure of the dose cohort in the multiple ascending dose portion is equal to or higher than the exposure of the dose determined to be the MTD after the single doses.

Dose Interruption

- If ALT or AST are increased $\geq 3 \times$ ULN, ALT and AST will be monitored at least weekly. If ALT or AST continues to rise ≥ 3 to $\leq 5 \times$ ULN prior to the next dose, the investigator and Sponsor will review the subject's clinical data prior to administering the next dose and dosing may be interrupted.
- Dosing will be interrupted in individual subjects when the following occurs:
 - a. Serum AST or ALT are increased to $>5 \times$ ULN (CTCAE Grade ≥ 3); confirmed within 7 days (by both local and central labs).
 - b. Confirm creatine kinase (CK) WNL and source of enzyme elevation is not muscle related.

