If ALT or AST elevation of $>5 \times$ ULN (CTCAE Grade ≥ 3) is confirmed, ALT and AST will be monitored weekly until liver enzymes have returned to WNL if subject was WNL at baseline; or to $<2 \times$ ULN if was between 1 – 2 \times ULN at baseline. Once ALT/AST levels have returned to WNL if subject was WNL at baseline; or to $<2 \times$ ULN if was between 1 – 2 \times ULN at baseline, the results must be confirmed within 7 days (by both local and central labs), at which point dosing may resume as scheduled per protocol. Missed doses will not be made up. If dosing is interrupted, all study visits and procedures will continue as per protocol, with the exception of dosing and subject will be followed to the end of the study.

If following the Day 1 dosing is interrupted due to ALT or AST elevation, the dosing windows for Day 29 or Day 57 may be extended to ± 2 days to allow for evaluation of ALT/AST.

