31. Positive human immunodeficiency virus (HIV) antibody, hepatitis B surface antigen (HBsAg), hepatitis B core antibody (HBcAb), or hepatitis C antibody tests indicative of present or prior infection.

NOTE: If a subject tests negative for HBsAg, but positive for HBcAb, the subject will be considered eligible if the subject tests positive for antibody to HB surface antigen (HBsAb or anti-Hbs).

32. AST or ALT >2xULN at Screening. If the subject participated in SAD, no ALT or AST elevation \geq 3xULN during the SAD.

33. Direct bilirubin >ULN.

34. TSH < LLN or > ULN.

35. Platelets < LLN or >450,000 U/uL.

36. Creatine kinase >2xULN.

37. Positive urine drug (illicit) screen (positive drug screen for prescription drugs, eg benzodiazepines, allowed if approved by Sponsor).

38. 12 lead ECG demonstrating QTc >450 msec or a QRS interval >120 msec at Screening. If QTc exceeds 450 msec, or QRS exceeds 120 msec, the ECG should be repeated two more times and the average of the three QTc or QRS values should be used to determine the subject's eligibility.

39. Any abnormal hematology values, clinical chemistries, urinalysis, or ECGs judged by the Investigator or Sponsor as clinically significant.

Other Exclusions:

40. Pregnant or breast-feeding women.

41. Men who are unwilling or unable to use a highly effective method of contraception as outlined in this protocol for the duration of the study and for at least 60 days after the last dose of investigational product.

42. Unwilling or unable to comply with the Lifestyle guidelines described in this protocol.

43. Other severe acute or chronic medical or psychiatric condition or laboratory abnormality that may increase the risk associated with study participation or investigational product administration or may interfere with the interpretation of study results and, in the judgment of the investigator, would make the subject inappropriate for entry into this study.

44. Subjects who are investigational site staff members directly involved in the conduct of the study and their family members, site staff members otherwise supervised by the Investigator, or subjects who are Pfizer employees directly involved in the conduct of the study.

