6.3.13. Day 29 - MAD

On Day 29, after an overnight fast of at least 10 hours, the following procedures will be completed **prior to study drug administration**:

- Obtain blood sample at approximately 03:00 AM and 07:30 AM (immediately prior to breakfast) for mean daily glucose profile.
- Assess symptoms by spontaneous reporting of adverse events and by asking the subjects to respond to a non-leading question such as "How do you feel?"
- Assess patency of peripheral IV (PIV)/heplock, in accordance with site policies,
 - If no longer patent remove and insert a new PIV/heplock in accordance with site policies. Allow subject to rest at least 1 hour prior to obtaining vital signs.
- Conduct limited physical exam of the skin, heart, lungs, abdomen and extremities by trained medical personnel at the investigator site.
- Collect fasting weight.
- Collect triplicate 12-Lead ECG.
- Obtain temperature, supine pulse rate and triplicate supine blood pressure. Blood pressure will be the only vital sign collected in triplicate.
- Obtain blood sample immediately prior to breakfast (fasting) to complete the mean daily glucose profile.
- Collect fasting blood and urine samples for safety labs (hematology, chemistry, urinalysis (clean catch, midstream)).
- Collect blood samples for:
 - Fasting lipid profile;
 - Apo B;
 - Coagulation panel, amylase and lipase;
 - HbA1c;
 - FPG, fasting glucagon and fasting GLP-1;

- Fructosamine;
- 1,5-anhydroglucitol;
- Pharmacokinetic analysis;
- ADA.
- Administer the study medication (see **STUDY TREATMENTS** and **Administration Sections**).

After dosing, the following procedures will be completed:

- Assess symptoms by spontaneous reporting of adverse events and by asking the subjects to respond to a non-leading question such as “How do you feel?”
- Injection site assessment immediately after injection at: 15 and 30 minutes, 1, and 2 hours post administration. Additional assessments should be performed as needed after the last assessment of 2 hrs post-dose on dosing days.
- Assess temperature, supine pulse rate and supine triplicate blood pressure at 1, 2, and 4 hours after dosing. Blood pressure is the only vital sign to be collected in triplicate.
- Obtain triplicate 12-lead ECG measurements at 1, 2, and 4 hours after dosing.
- Collect blood samples for pharmacokinetic analysis at 1 and 4 hours following dosing.
- Record concomitant medications.
- Question subject on metformin compliance.
- Remove PIV/heplock prior to discharge.

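### Protocol Section 3.3 does not settle whether a MAD dose must wait while an ALT/AST value above 5×ULN is unconfirmed; on one reading neither a hold nor a pre-dose review is required

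*Protocol*

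**What the plan says.** The rules are in protocol Section 3.3, under Dose Interruption.

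- **From 3×ULN:** ALT and AST are followed at least weekly. If they keep rising between 3 and 5×ULN before the next dose, the investigator and sponsor must review the subject's "clinical data prior to administering the next dose and dosing may be interrupted".
- **Above 5×ULN:** interruption is mandatory. Item (a) gives the threshold and, after a semicolon, "confirmed within 7 days (by both local and central labs". Item (b) reads "Confirm creatine kinase (CK) WNL and source of enzyme elevation is not muscle related".
- **After confirmation:** once the elevation "is confirmed, ALT and AST will be monitored weekly until liver enzymes have returned to WNL if subject was WNL at baseline" (or to below 2×ULN for subjects between 1 and 2×ULN at baseline). The recovery must itself be confirmed, "at which point dosing may resume as scheduled per protocol. Missed doses will not be made up".
- **Window:** the last paragraph of Dose Interruption and footnote q of the MAD Schedule of Activities allow, but do not require, the Day 29 or Day 57 dosing window to be widened to 2 days either side. Footnote q gives the purpose as "to allow for evaluation of ALT/AST if subject experiences" a value of at least 3×ULN after the Day 1 dose. It sets no upper cap and does not require confirmation.

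On Day 29 the pre-dose list includes "Collect fasting blood and urine samples for safety labs (hematology, chemistry, urinalysis (clean catch, midstream" (Section 6.3.13). Day 57 has the same item (Section 6.3.16). Exclusion criterion 36 is "Creatine kinase >2xULN".

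**The concern.** No sentence says what happens to a dose that falls due between a first value above 5×ULN and its confirmation. If interruption starts only at confirmation, the requirements are out of order: a subject rising at 4×ULN is guaranteed a review before dosing, while one at 6×ULN awaiting confirmation is guaranteed neither a review nor a hold. The window extension does not repair this, because it is optional and shorter than the time allowed for confirmation.

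At stake is whether a subject with a possible Grade 3 liver signal receives another subcutaneous antibody dose, which cannot be taken back. Section 1.3.2 reports peak concentration about 4 to 10 days after a single SC dose and a half-life of 9 to 18 days over 0.3 to 3 mg/kg. If dose 2 is given on Day 29, a confirmation on Day 36 comes 7 days later, inside that peak range.

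Item (b) is a smaller ambiguity. It stands in the list of triggers, yet criterion 36 admits subjects with CK up to 2×ULN, who may not have a normal CK at baseline. The rules for a confirmed elevation do not mention CK. A site could therefore be unsure whether a raised CK cancels the hold.

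**Working it through.** The plan gives no figure of its own on this point, so there is none to reproduce. The check compares the two readings and then does the day arithmetic.

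**The two readings of item (a)**

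- *Interrupt, then confirm.* The semicolon separates the threshold from the confirmation. The last paragraph of Dose Interruption describes dosing already interrupted for an ALT/AST elevation, with the window widened so that it can be evaluated. Where confirmation is a precondition, as for resuming, the text says so directly.
- *Interrupt once confirmed.* The confirmation phrase sits inside the criterion. The follow-up and resumption rules start from a confirmed elevation, and no rule covers an elevation that fails confirmation.

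The text does not decide between them.

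**Day arithmetic under the second reading**

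Inputs: dose days D = 29 and 57 (Section 3.1); confirmation limit 7 days (Section 3.3), counted here from sampling; extended window closes at D + 2 (Section 3.3, footnote q).

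For a first value above 5×ULN sampled k days before the nominal dose day:

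- confirmation limit = D − k + 7
- gap after the extended window closes = max(0, (D − k + 7) − (D + 2)) = max(0, 5 − k)

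| k | Dose 2: sample, limit, window closes | Dose 3: sample, limit, window closes | Gap (days) |
|---|---|---|---|
| 0 | 29, 36, 31 | 57, 64, 59 | 5 |
| 1 | 28, 35, 31 | 56, 63, 59 | 4 |
| 2 | 27, 34, 31 | 55, 62, 59 | 3 |
| 3 | 26, 33, 31 | 54, 61, 59 | 2 |
| 4 | 25, 32, 31 | 53, 60, 59 | 1 |
| 5 or more | | | 0 |

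With the extension, the exposed sampling days are 25–29 and 53–57. Without it, Day 29 has no visit window (Section 6.3.13), so the limit is still open when D − k + 7 > 29, that is Days 23–29. Day 57 has ±1 day (Section 6.3.16), so the condition is D − k + 7 > 58, that is Days 52–57.

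**Laboratory turnaround.** The documents do not state it. For a result to be known by the nominal dose time after a turnaround of L days, k must be at least L, so the largest gap is 5 − L: 5, 4 or 3 days for assumed turnarounds of 0, 1 or 2 days. If the result returns after dosing, no hold rule can act on that dose.

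**Which samples can cause this.** The previous scheduled chemistry panels are on Days 15 and 43. Their limits are 15 + 7 = Day 22 and 43 + 7 = Day 50, both before the next dose. The exposed samples are therefore the dosing-day panel and any weekly-monitoring or unscheduled sample in the days before it. Weekly follow-up from Day 15 falls on Days 22 and 29, and from Day 43 on Days 50 and 57.

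**The case against.** The strongest objection is that the protocol already means interrupt first and confirm afterwards. The semicolon and the window paragraph support this. If the hold began only at confirmation, a 2-day extension would do little for such a subject, since resumption then needs recovery and a second confirmation. The extension fits best with a hold on an elevation still under evaluation, although it could also serve a discretionary interruption at 3 to 5×ULN. This much stands: a reader might infer that the protocol stops dosing only after confirmation, or directs sites to dose an unconfirmed Grade 3 value, and the documents support neither as settled fact.

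The second objection is that the situation is hard to reach. Dosing is at about 08:00 (Section 5.2.4) and safety tests go to a central laboratory (Section 7.2.1), so a same-day result before dosing may be unusual. Subjects under weekly monitoring are already known to be at 3×ULN or more and are already reported as adverse events (Section 8.4). If they rose through 3 to 5×ULN, the mandatory review had been triggered. Seven days is also a maximum, and confirmation may be quicker. All of this stands as a limit on size.

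Third, other safeguards exist: unblinded sponsor staff interpreting safety data in real time (Section 5.2), withdrawal at the investigator's or sponsor's discretion (Section 6.4), and the Hy's Law work-up (Section 8.5.2). They make an unsafe re-dose less likely, but none says that the dose waits.

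**Conclusion.** The point holds as an ambiguity with a safety consequence on one of two tenable readings. On that reading, an unconfirmed value above 5×ULN on a re-dosing day carries no mandatory hold and no mandatory review, and the optional extension falls short of the confirmation limit by up to 5 days. That figure assumes a first sample no later than the nominal dose day, 7 days counted from sampling, and a result known before dosing.

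The number of doses affected cannot be estimated. SAP Table 2 gives 8 + 16 + 8 = 32 active and 2 + 4 + 2 = 8 placebo subjects, so at most 40 × 2 = 80 re-dose decisions (64 active, 16 placebo) if every subject reaches both. The documents give no rate of unconfirmed elevations at those times, and nothing on how often an investigator would go ahead. The number is probably very small. A reader might infer that subjects would in practice be re-dosed with a Grade 3 value pending; the text shows only that the plan does not clearly rule this out. It merits correction because the rule governs an irreversible act and is cheap to clarify.

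**What to change.** Amend Section 3.3 to state that:

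1. The next dose is withheld from the first ALT or AST value above 5×ULN until confirmation is complete. If the dosing window closes first, the dose is skipped, in line with the existing rule on missed doses.
2. Review by the investigator and sponsor before the next dose is mandatory for any ALT or AST of 3×ULN or more, with no upper cap.
3. When a dose is due, the repeat sample is taken as soon as possible. This should not be presented as ensuring confirmation inside the window: turnaround is unstated, and both laboratories must confirm. The 48-hour interval in Section 8.5.2 is only a preference, applies to potential Hy's Law cases, and runs from awareness of the result.
4. CK is measured to attribute the elevation and is not a condition for the hold.

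This is a few sentences and adds no scheduled visit. The cost is that an occasional dose is delayed or skipped for a value that is later not confirmed. A skipped dose removes one of three for that subject and loses some Day 57 PK information in a dose group of 8 or 16 active subjects.

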3.3.1. Toxicity Criteria

Table 7. Toxicity Criteria

Parameter	Definition ¹
Serious adverse event	Serious adverse event;
Increased liver transaminases ²	Serum AST ³ and/or ALT ⁴ are both increased to $>5 \times \text{ULN}^5$ (CTCAE ⁶ Grade ≥ 3);
Increased direct bilirubin ² (in absence of ALT/AST elevations)	Adapted from CTCAE ⁶ Grade ≥ 2 ;
Hypoglycemia	One (1) subject experiences ≥ 2 hypoglycemic events of <40 mg/dL (CTCAE ⁶ Grade ≥ 3) which do not meet SAE criteria;
Pancreatitis	Severe pain, vomiting; medical intervention indicated (CTCAE ⁶ Grade ≥ 3);
Decreased platelet count ²	Thrombocytopenia to $<100,000/\mu\text{L}$ [$<100 \times 10^9/\text{L}$];
Hypertriglyceridemia ²	>1000 mg/dL (CTCAE ⁶ Grade ≥ 4);
Increased serum creatinine ²	Serum creatinine to $2.2 \times \text{ULN}^5$ (CTCAE ⁶ Grade ≥ 3);
Diarrhea, enteritis or nausea	Increase of >6 stools/day over baseline; incontinence; hospitalization indicated; inadequate oral caloric or fluid intake (CTCAE ⁶ Grade ≥ 3);
ECG changes from baseline	Clinically significant ECG change from baseline including but not limited to interval changes (eg, PR, QTcF), ST-T wave changes, appearance of Q waves, atrial or ventricular rhythm abnormality, QRS axis deviation or ventricular conduction defect associated with clinical symptoms;
Prolongation of QT _c F interval ^{2,7}	QT _c F >500 msec (ie, CTCAE ⁶ Grade ≥ 3) or increase from baseline of ≥ 60 msec;
Unspecified	If considered appropriate by the medical monitor and investigator.

1. Unless considered to be unrelated to study medication by Investigator and Sponsor.
 2. To be confirmed by a repeat test.
 3. AST = aspartate aminotransferase.
 4. ALT = alanine aminotransferase.
 5. ULN = upper limit of normal reference range of the clinical laboratory.
 6. CTCAE = Common Terminology Criteria for Adverse Events.
 7. QT_cF = QT interval (Fridericia's correction).

In the event that a subject develops any of the toxicities outlined in Table 7, the subject will be followed until resolution and/or referred to an appropriate specialist

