8.5.2. Potential Cases of Drug-Induced Liver Injury

Abnormal values in aspartate aminotransferase (AST) and/or alanine aminotransferase (ALT) levels concurrent with abnormal elevations in total bilirubin level that meet the criteria outlined below in the absence of other causes of liver injury are considered potential cases of drug-induced liver injury (potential Hy's Law cases) and should always be considered important medical events.

The threshold of laboratory abnormalities for a potential case of drug-induced liver injury depends on the subject's individual baseline values and underlying conditions. Subjects who present with the following laboratory abnormalities should be evaluated further to definitively determine the etiology of the abnormal laboratory values:

- Subjects with AST or ALT and total bilirubin baseline values within the normal range who subsequently present with AST or ALT values ≥ 3 times the upper limit of normal (X ULN) concurrent with a total bilirubin value ≥ 2 X ULN with no evidence of hemolysis and an alkaline phosphatase value ≤ 2 X ULN or not available.
- For subjects with preexisting ALT **OR**, AST **OR** total bilirubin values above the upper limit of normal, the following threshold values should be used in the definition mentioned above:
 - For subjects with pre-existing AST or ALT baseline values above the normal range: AST or ALT values ≥ 2 times the baseline values and ≥ 3 X ULN, or ≥ 8 X ULN (whichever is smaller).
- **Concurrent with**
 - For subjects with pre-existing values of total bilirubin above the normal range: Total bilirubin level increased from baseline by an amount of at least one time the upper limit of normal or if value reaches ≥ 3 times the upper limit of normal (whichever is smaller).

The subject should return to the investigational site and be evaluated as soon as possible, preferably within 48 hours from awareness of the abnormal results. This evaluation should include laboratory tests, detailed history and physical assessment. In addition to repeating measurements of AST and ALT, laboratory tests should include albumin, creatine kinase, total bilirubin, direct and indirect bilirubin, gamma-glutamyl transferase (GGT), prothrombin time (PT)/ international normalized ratio (INR), and alkaline phosphatase. A detailed history, including relevant information, such as review of ethanol, acetaminophen, recreational drug and supplement consumption, family history, occupational exposure, sexual

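### Table 7 drops its direct bilirubin row once ALT/AST is elevated but never defines elevated; on two of three readings a worse liver picture meets no objective row

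*Protocol*

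**What the plan says.** Protocol Section 3.3.1, Table 7, lists the toxicities used in escalation decisions. Four rows matter here.

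- **Direct bilirubin:** an adapted CTCAE Grade 2 or higher, confirmed by repeat test, but only "in absence of ALT/AST elevations". No multiple of ULN is attached to the word elevations.
- **Transaminases:** AST and/or ALT "are both increased to" more than 5xULN, confirmed by repeat test.
- **Serious adverse event:** any SAE. Section 8.5.2 brings confirmed potential Hy's Law cases in here.
- **Unspecified:** "If considered appropriate by the medical monitor and investigator".

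A listed event counts unless the investigator and the sponsor consider it unrelated to study drug.

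Section 3.3 uses these toxicities under the statement "Dose escalation will be terminated based on the following criteria". The first criterion is two or more subjects on active drug with similar clinically significant abnormalities, or with severe adverse events in one organ class. That rule cites Table 3, which is a dose and safety-margin table; I take it to mean Table 7. Section 3.1 also uses Section 3.3.1 to define the acute toxicity that holds back the rest of each SAD cohort after its first two subjects.

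At entry (Section 4.2), subjects are excluded for "AST or ALT >2xULN at Screening" and for "Direct bilirubin >ULN". A subject may therefore start with ALT/AST above normal, but not with raised direct bilirubin.

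**The concern.** A bilirubin rise together with transaminase injury is a worse sign than the same rise alone. Table 7 can treat it the other way round. The isolated rise has its own row; once ALT/AST is also elevated, that row no longer applies. Unless another row takes over, the more worrying subject drops out of the objective count towards the two-subject rule.

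This row is also the only objective decision criterion based on direct bilirubin after entry. Dose interruption (Section 3.3) and extended liver follow-up (Section 6.3.29) use enzymes. Section 8.5.2 and SAP Section 10.2.2.4 use total bilirubin.

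**Working it through.** **Plan figure.** The nearest is Table 10 in Protocol Section 9.1, the probability of two or more SAEs: P = 1 - (1-p)^n - n·p·(1-p)^(n-1). At p = 0.20, n = 6 gives 1 - 0.26214 - 0.39322 = 0.34464 (plan 0.34), and n = 8 gives 1 - 0.16777 - 0.33554 = 0.49669 (plan 0.50). All 14 entries agree within 0.01. The table concerns SAEs and does not size this gap.

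**Routes other than the bilirubin row.**

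1. Transaminase row: needs more than 5xULN, so it cannot catch 1 to 5xULN.
2. SAE row through Section 8.5.2, normal baselines: ALT or AST at least 3xULN and total bilirubin (TB) at least 2xULN, "with no evidence of hemolysis and an alkaline phosphatase value" of at most 2xULN or not available, and no other cause found.
3. For a raised enzyme baseline b (in xULN), the Section 8.5.2 enzyme threshold is min(max(2b, 3), 8). So b = 1.5 gives 3.0, b = 1.8 gives 3.6 and b = 2.0 gives 4.0.

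**Three readings of an elevation.** Literal: any value above ULN. At least 3xULN: the cut-off in Sections 3.3 (monitoring), 4.2 (exclusion 32, for former SAD subjects), 6.3.29 and 8.4. More than 5xULN: the Table 7 row above.

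**Illustrative cases.** Each has a confirmed, drug-related direct bilirubin rise meeting the adapted grade, no hemolysis and no other cause. Values are in xULN; ALP is alkaline phosphatase. Baselines are normal except in F. *Yes* means an objective row is met.

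| Case | Literal | ≥3x | >5x |
|---|---|---|---|
| A: ALT 0.9, TB 1.8 | yes | yes | yes |
| B: ALT 1.2, TB 1.8 | no | yes | yes |
| C: ALT 4, TB 1.8, ALP 1 | no | no | yes |
| D: ALT 4, TB 2.5, ALP 2.5 | no | no | yes |
| E: ALT 4, TB 2.5, ALP 1 | yes (8.5.2) | yes (8.5.2) | yes |
| F: ALT 2.0 at baseline, now 3.5; TB 2.5, ALP 1 | no | no | yes |
| G: ALT 6, AST 3, TB 1.8 | doubtful | doubtful | doubtful |

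A against B and C shows the reversal: the same bilirubin rise counts with normal ALT and can stop counting at ALT 1.2 or 4. In F the enzyme threshold is 2 x 2.0 = 4.0, so 3.5 falls short even though TB is above 2xULN.

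G turns on the transaminase row, whose text joins and/or with both. Read as either enzyme, G counts. Read strictly as both, it does not meet that row. The MAD dose-interruption rule in Section 3.3 is worded differently: "Serum AST or ALT are increased to" more than 5xULN.

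**Ranges with no objective row (normal baselines).**

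- Literal: above 1x to below 3xULN at any TB, plus 3 to 5xULN when Section 8.5.2 is not met.
- At least 3xULN: 3 to 5xULN when Section 8.5.2 is not met.
- More than 5xULN: none between 1x and 5xULN.

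**The case against.** The strongest reply is that the two liver rows are a pair. The row above sets the transaminase toxicity at more than 5xULN, so an absence of elevations naturally means that row is not met. The literal reading also fits poorly with Sections 3.3 and 6.3.29, which accept below 2xULN as recovered for subjects who entered between 1x and 2xULN. This stands as a plausible intention, and on it the gap between 1x and 5xULN disappears. But the row does not say so. The protocol uses 3xULN for several other liver decisions, and sites could apply the row differently.

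The second reply is that escalation is not automatic. SAD progression requires a well-tolerated dose and a satisfactory safety review. MAD escalation needs a joint decision, and reaching the limit of tolerability is itself a termination criterion. The sponsor cannot override an investigator who stops. ALT or AST of at least 3xULN is reported as an adverse event (Section 8.4), and the sponsor can upgrade an event to serious (Section 8.1). All of this stands and lowers the severity. These routes rely on judgement, however, and do not restore an objective bilirubin count.

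Third, SAP Section 3 records that doses above the 150 mg cohort were judged unnecessary and that later MAD work used 50 mg and an expanded 75 mg cohort. That limits the practical effect on escalation from then on.

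Two stronger readings might be inferred, and the documents support neither. One is that every bilirubin rise with ALT/AST up to 5xULN escapes the rule: potential Hy's Law cases count as SAEs (case E), and the >5xULN reading leaves no gap there. The other is that a single enzyme above 5xULN never counts. That is doubtful only if both is read strictly. Even then, Sections 3.3 and 8.7 make more than 5xULN a Grade 3, severe event, so it may count through the limb on severe adverse events in one organ class.

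**Conclusion.** The point holds as an ambiguity with a real safety consequence on two of three readings. On those readings, a confirmed, drug-related direct bilirubin rise that would count alone meets no objective Table 7 row when ALT/AST is above 1x to below 3xULN (literal only), or 3 to 5xULN outside Section 8.5.2. It then counts only through the Unspecified row or a judgement that the event is serious, or leads to a discretionary stop.

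The conclusion assumes that the rule's Table 3 means Table 7, and the ranges assume normal baselines. A reader might want a figure for the lost chance of stopping. None can be given: the documents state neither how often direct bilirubin would rise nor what share of rises would come with raised ALT/AST. Severity is minor to moderate.

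**What to change.** Delete the words "in absence of ALT/AST elevations" and their brackets from the direct bilirubin row of Table 7. A confirmed, drug-related rise then counts whatever the ALT/AST value, and cases A to G all meet that row. No count-once footnote is needed, because the two-subject rule already counts subjects.

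Writing more than 5xULN into the qualifier would also settle its meaning, but would leave case G in doubt. Deletion does not clarify a single enzyme above 5xULN without a bilirubin rise, or supply the number behind the adapted CTCAE grade. The sponsor could settle both in the same edit; the documents do not give that number.

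The cost is one phrase. Direct bilirubin is already in the chemistry panel (Table 9) and in the MAD Day 36 and Day 64 liver tests, so no new test, visit, subject or SAP change is needed. The downside is that the escalation-termination rule may be met slightly more often, by an amount the documents do not allow anyone to state.
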